4	Partograph Extraction tool (revised July 2017)	There are sections where the data extractors will enter the information on the woman and newborn conditions and outcomes that appears a) at the top of the partograph, b) at the bottom of the partograph and c) provider actions recorded on the Jhpiego stamp tool. There are repeatable sections that also allow for data entry on the actual values of the measurements are recorded for 13 parameters (fetal heart rate, cervical dilation, systolic and diastolic blood pressure, amniotic fluid, moulding, head descent, contractions, pulse, temperature, urine protein, acetone and volume). These data will be recorded for each 30 minute interval for the duration of the active stage of labor (4cm dilation to 10cm dilation).
5	Register review tool	This tool will contain the abstracter id, date and facility id, month number of deliveries, Live births (spontaneous, assisted, cesarean, breech), fresh stillbirths, macerated stillbirths, number of twins, early neonatal deaths, number referred, number of maternal deaths
6	Qualitative discussion field guide for ePartogram sites (in-depth interviews or small focus groups)	Qualitative interviews will be conducted with providers in each study arm. In the ePartogram group, qualitative interviews will be administered to better understand the benefits and challenges of ePartogram. Providers will be asked about their experience in using the ePartogram, opinions on various features of the application, and implementation considerations for ePartogram.
7	Qualitative discussion field guide for paper partograph sites (in-depth interviews or small focus groups)	Qualitative interviews will be conducted with providers in the paper partograph group to better understand how providers use the paper partograph in a variety of labor and delivery settings, perceived benefits and challenges in using paper partograph, and the facility conditions that enable or hinder adoption of best practices in labor management

(a) Existing tool already in use

2. Describe the **number and type of study visits and/or contacts** between the study team and the participant, how long they will last, and where/how they will take place.

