
P1. Compliance with globally-recommended labor monitoring practices and recording on the partograph of the information obtained – complete on admission (Tool 4)
	
We will examine each parameter and enter to the database.
 
Overall, this will be marked ‘yes’ if 11 of the 12 items (all except urine volume) are measured at admission (fetal heart rate, cervical dilation, systolic and diastolic blood pressure, amniotic fluid, moulding, head descent, contractions, pulse, temperature, urine protein, acetone and volume); and otherwise ‘no’. Binary variable.
	
All labors with partograph or ePartogram
 
Unit of analysis is each case (partograph).
	
First, we will examine the frequency/prevalence of each measurement recorded on admission and compare between the two study groups
 
Second, We will examine the percent of cases marked ‘yes’ (defined at left). Independent variable is study group. Bivariate analysis will be an unadjusted logistic regression accounting for clustering in the facility or in the provider. In multivariable analysis, other control factors added may be facility type, client volume, region or provider variables.

- Complete over entire labor (Tool 4)
	
We will examine each parameter and enter to the database. Then we will see how many hours was the labor for the appropriate frequency, per the Jhpiego Clinical Rules and determine whether this was done to a large extent on time.
 
Overall, this will be marked ‘yes’ if 11 of the 12 items (all except urine volume) are measured in first 4-hour period at the specified intervals (reviewer will determine for each item if occurred within the interval): fetal heart rate every 30 min, cervical
	
All labors with partograph or ePartogram
	
Same as above – except it will be for the first four hour period

	dilation every 4 hours, systolic and diastolic blood pressure every 4 hours, amniotic fluid if membranes rupture, moulding when present head descent every 2 hours, contractions every 30 min, pulse every 30 min, temperature every 2 hours, urine protein, acetone and volume, all at every 4 hours. ; and otherwise ‘no’. Binary variable.		
- Complete over entire labor for a subset of women who arrived at 4 or 5 cm			

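### The P1 outcome labelled as complete over the entire labor is scored only on the first 4 hours, so a labor left blank after hour 4 is still marked 'yes'

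*Combined protocol and SAP*

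**What the plan says.** Section V.C.4, Table 5, gives P1 three rows. The first scores completeness on admission. The second is labelled "Complete over entire labor", and its cases are all labors with a partograph or ePartogram.

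- **Outcome cell, lead-in.** The plan says "Then we will see how many hours was the labor for the appropriate frequency, per the Jhpiego Clinical Rules" and that the team will "determine whether this was done to a large extent on time". No threshold is attached to either statement.
- **Outcome cell, rule.** A case is 'yes' if 11 of 12 items (urine volume is left out) "are measured in first 4-hour period at the specified intervals", and 'no' otherwise. The intervals follow: for example "fetal heart rate every 30 min", head descent every 2 hours, cervical dilation every 4 hours. Amniotic fluid and moulding are conditional.
- **Analysis cell.** The analysis is the same as for the admission outcome, "except it will be for the first four hour period".

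The third row carries the same whole-labor label for women arriving at 4 or 5 cm. In the text available it has no outcome, cases or analysis of its own.

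Table 4 (Tool 4) describes what is extracted for the 13 partograph parameters: "These data will be recorded for each 30 minute interval for the duration of the active stage of labor", defined as 4 cm to 10 cm dilation. The statistical analysis plan paragraph after Table 5 says that every outcome will be a yes/no variable.

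**The concern.** The label promises a statement about the whole labor, and the rule delivers one about its first 4 hours. A result reported under the label would be read as showing that monitoring was kept up until the end of labor, and the variable cannot show that.

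P1 is a primary research question, and section I says the study is to inform the Ministry of Health on whether to use the ePartogram more widely. Section I also lists prolonged labor, including labor over 12 hours, among the complications of interest. The unscored part grows with the length of labor, so it is largest in those cases. If the arms differ in how well monitoring is sustained after hour 4, this outcome cannot detect it. If they differ only early, the label would overstate how far the difference extends.

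**Working it through.** The plan gives no figure for this outcome and no sample size for P1, so there is nothing of the plan's own to reproduce. The check has two parts.

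**1. Label against rule.** The label says entire labor. The Outcome cell's rule and the Analysis cell both say first 4 hours. The two operative cells agree with each other, so the 4-hour window is the definition, not a slip in one cell. The lead-in sentence points towards the length of labor but creates no variable.

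Nothing else in P1 reaches past hour 4. The first row covers admission only. The third row has no definition, and if it is meant to inherit the row above, it inherits the 4-hour window too. P2 and P3 score clinical actions, not completeness of recording.

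**2. Share of scheduled readings that is scored.** The inputs are the intervals in the Table 5 rule. With blood pressure as one item and urine volume left out, nine items have fixed intervals:

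- every 30 minutes: fetal heart rate, contractions, pulse (3 items)
- every 2 hours: head descent, temperature (2 items)
- every 4 hours: dilation, blood pressure, urine protein, acetone (4 items)

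With one slot per completed interval, the slots due in T hours are 3 × (T/0.5) + 2 × (T/2) + 4 × (T/4), each quotient rounded down.

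- T = 4: 3×8 + 2×2 + 4×1 = 32
- T = 8: 3×16 + 2×4 + 4×2 = 64
- T = 12: 3×24 + 2×6 + 4×3 = 96

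| Recorded labor | Fetal heart rate slots due | All slots due | Slots scored | Share scored |
|---|---|---|---|---|
| 4 h | 8 | 32 | 32 | 100% |
| 6 h | 12 | 46 | 32 | 70% |
| 8 h | 16 | 64 | 32 | 50% |
| 10 h | 20 | 78 | 32 | 41% |
| 12 h | 24 | 96 | 32 | 33% |

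The labor lengths are illustrative. Only 12 hours comes from the documents, as the prolonged-labor threshold. In a 12-hour labor, 24 − 8 = 16 fetal heart rate slots can be empty and the case is still marked 'yes'.

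**What the rule leaves open.** Three points are undefined:

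- Records shorter than 4 hours are included in the cases, but no scoring rule is given for them.
- A 4-hourly item has one slot in the window. The plan does not say whether the admission reading fills it or a reading near hour 4 is needed.
- The lead-in's tolerance for timing is not tied to the yes/no rule, so it is unclear whether one late half-hourly reading fails an item.

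**The case against.** The window may be deliberate. It stands in both operative cells of a table marked as updated in July 2017. A fixed window gives every labor of at least 4 hours the same number of readings to meet, whereas an all-or-nothing rule over the whole labor would be harder to pass the longer the labor lasts. On this view only the label is wrong, and renaming the row cures it. The P1 question in section I asks about compliance with recommended monitoring and does not itself say entire labor, so admission and first-4-hour completeness are partial but relevant answers.

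Much of this stands. The 4-hour outcome is worth keeping, and P1 is not left unanswered. Renaming alone, however, would leave P1 with no measure of monitoring after hour 4, although Table 5 evidently meant to have one and the data are extracted.

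A reader might infer four stronger things that the documents do not support:

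- *Repeat measurement of 4-hourly items is never tested.* The plan leaves it to the reviewer whether each item occurred within its interval, so this is ambiguous, not established.
- *Short labors cannot be scored.* The lead-in mentions the hours of labor, which may imply an adjustment. The handling is unspecified, not impossible.
- *The rule is so strict that few labors could pass.* That needs an on-time rate, a per-item tolerance and an assumption about how misses cluster. The documents give none of these, and the three half-hourly items fall due together, so misses probably coincide.
- *Reminders help most late in labor, so a real effect will be missed.* The protocol describes reminders without any such gradient. The direction of any bias is unknown.

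**Conclusion.** The concern holds as a mismatch between label and rule in a primary outcome, with a resulting gap in what P1 measures. The mismatch is certain from Table 5 itself. 'Yes' on this variable means the rule was met in the first 4 hours and nothing more.

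The outcome scores half of the scheduled slots in an 8-hour labor and a third in a 12-hour labor. These shares assume one slot per interval over the nine fixed-interval items and leave out the conditional items. For records of about 4 hours there is little or no gap. The documents give no distribution of labor length and no monitoring rates, so neither the share of labors affected nor the change in the percentage marked 'yes' can be computed.

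This should be changed before analysis, because it alters what P1 can conclude. It does not invalidate the 4-hour outcome under an accurate name.

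**What to change.** 1. Rename the current binary outcome 'complete in first 4 hours'. State how records shorter than 4 hours are scored, whether the admission reading alone satisfies a 4-hourly item, and what timing tolerance, if any, applies to each item.
2. Add a whole-labor outcome: for each labor, the proportion of due readings that were recorded. Start at the first active-stage reading (4 cm or more), because Tool 4's interval data begin there. Stop at 10 cm or the end of the record (delivery, cesarean or transfer). Count only readings due in that labor, and conditional items only when they apply.
3. Analyse the proportion with a clustered model, for example GEE with a binomial or fractional logit, and amend the sentence after Table 5 that makes every outcome yes/no. Alternatively, prespecify a threshold on the proportion and keep the planned logistic model.
4. Apply the same definition to the row for women arriving at 4 or 5 cm, with its cases and analysis written out.

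The cost is SAP wording, some programming and one additional P1 outcome. No new data collection is needed, since Tool 4 already extracts values every 30 minutes through the active stage.

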JHSPH IRB Research Plan for New Data Collection

PI Name: [name], Medical Director and Vice President, Innovations Jhpiego/Baltimore

Co-Investigators: [name], [name], [name], [name], [name], [name]

Study Title: ePartogram Effectiveness Study in Kenya

IRB No.: 6958

PI Version No./Date: July 14, 2017, v4

I. Aims of the Study: Describe the aims/objectives of the research and/or the project's research questions or hypotheses.

The study aim is to measure the effectiveness of use of the electronic partogram vs. the standard-of-care paper partograph on labor management outcomes and labor outcomes in maternity wards in Kenya.

Research Questions

Primary

Comparing facilities in which birth attendant/providers are using the ePartogram and facilities in which providers are using the paper partograph, are the following improved?: [\(partograph review\)](#)

- P1) compliance with globally-recommended, labor monitoring practices and recording on the partograph of the practices performed
- P2) decision-making and actions taken to maintain normal labor
- P3) detection, decision-making and action to address deviations from normal labor and complications arising during labor

Complications of interest are: prolonged labor (labors over 12 hours or labor that crosses the action line, may not be over 12 hours), arrest of descent/dilation that precedes obstructed labor; obstructed labor including arrest of descent/dilation, fetal distress and maternal distress; maternal infection; severe pre-eclampsia or eclampsia; fetal distress; and maternal distress with shock-like symptoms.

Secondary

In intervention and control sites:

S1) Is facility use of ePartogram (vs. paper-partograph) associated with **lower rate of** (neonatal death <24 hours and intrapartum death (fresh stillbirth rate)? [\(register review\)](#)

S2) What **facility conditions** and practices enable or hinder implementation of best practices in labor monitoring and decision-making? What makes the partograph/ePartogram easy-to-use? Efficient? [\(qualitative inquiry, facility assessment\)](#)

S3) What is the availability, accessibility, acceptability, and quality of **supervision/support** provided with eSupervision connectivity and referral functions of the partogram? [\(qualitative inquiry\)](#)

This study will inform the Ministry of Health on the effectiveness of the ePartogram and whether to use it more widely in Kenya.

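### The P1 outcome labelled as covering the entire labor is scored only in the first 4 hours, a window equal to a single interval of the 4-hourly items

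*Combined protocol and SAP*

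**What the plan says.** Table 5 of the Data Analysis Plan (Section V.C.4) splits P1, a primary research question, into completeness on admission and a row titled "Complete over entire labor". In the second row a case is a yes if 11 of 12 items, all but urine volume, "are measured in first 4-hour period at the specified intervals". The Analysis cell agrees: "Same as above – except it will be for the first four hour period".

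The same cell sets the intervals. Fetal heart rate, contractions and pulse are half-hourly; head descent and temperature are 2-hourly. The slowest items are "dilation every 4 hours, systolic and diastolic blood pressure every 4 hours" and "urine protein, acetone and volume, all at every 4 hours". Amniotic fluid and moulding depend on events. The reviewer judges, item by item, whether a reading fell inside its interval.

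An earlier sentence in the cell speaks of the length of the labor and of whether monitoring was largely on schedule, but attaches no threshold or scoring rule. A further row, for women arriving at 4 or 5 cm, shows no entries in its outcome, cases or analysis cells.

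The extraction tool (Section V.C.1, Table 4, Tool 4) covers more than the first 4 hours: "These data will be recorded for each 30 minute interval for the duration of the active stage of labor", that is, from 4 cm to 10 cm.

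**The concern.** The label promises whole-labor completeness and the rule delivers the first 4 hours. Because the outcome and analysis cells agree on 4 hours, an analyst following the plan would report as whole-labor completeness something that was not measured.

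The length of the window adds a second difficulty. It equals exactly one interval of the 4-hourly items, so for those items the outcome may add nothing to the admission outcome.

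This bears on the trial's purpose. Reminders for the next measurement are a listed ePartogram feature (Section II). The background survey cited there found partographs started at the correct time in more than 90% of the cases in which they were used, but all components completed in only 58%. The weakness described is continued recording, and continued recording beyond hour 4 is what the score leaves out. Prolonged labor is a named complication of interest in Section I, and P1 would say nothing about monitoring late in such labors.

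**Working it through.** The plan states no figure for this outcome, so there is nothing to reproduce. The check counts readings due.

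**Inputs, all from the P1 rows of Table 5.** Window W = 4 h. Intervals i = 0.5 h (3 items), 2 h (2 items) and 4 h (4 items: dilation, blood pressure counted once, urine protein, acetone). With the 2 event-driven items this makes 3 + 2 + 4 + 2 = 11 scored items.

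**Formula.** The plan does not say when the clock starts or which endpoint counts, so three conventions are used:

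- hour 0 counts, hour W does not: W/i, rounded up
- hour 0 does not count, hour W does: W/i, rounded down
- both count: W/i rounded down, plus 1

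**Readings due in the 4-hour window**

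| Interval | Hour 0 only | Hour 4 only | Both |
|---|---|---|---|
| 0.5 h | 8 | 8 | 9 |
| 2 h | 2 | 2 | 3 |
| 4 h | 1 | 1 | 2 |

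**What this means for the 4-hourly items.**

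- Hour 0 counts alone: the single reading due is the admission reading, already scored in the first P1 outcome. No repeat is tested.
- Only readings after admission count: one reading is due by hour 4, so the first repeat is tested.
- Both endpoints count: 2 are due, and again the first repeat is tested.
- Under every convention, later repeats are outside the score.

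**Against a longer labor (hour 0 counts, hour W does not).** The 8 h and 12 h durations are illustrations and assume that all those hours are under observation and within the extracted period.

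| Interval | Scored in 4 h | Due in 8 h | Due in 12 h |
|---|---|---|---|
| 0.5 h | 8 | 16 | 24 |
| 2 h | 2 | 4 | 6 |
| 4 h | 1 | 2 | 3 |

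The scored share is 4/8 = 50% at 8 hours and 4/12 = 33% at 12 hours. At 12 hours, 24 − 8 = 16 half-hour slots go unscored, as do 3 − 1 = 2 of the 3 rounds of each 4-hourly item (those due at hours 4 and 8).

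**The case against.** The strongest reply is that the rule is stated consistently in two cells, so the planned analysis is largely identifiable. A fixed window also gives every labor that reaches 4 hours the same observation time. Both points are fair. They support keeping the rule under an accurate name; they do not support the present label. The sentence about length of labor suggests that a whole-labor assessment and some tolerance on timing were intended, but without a scoring rule it cannot override the explicit one.

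Four stronger readings are tempting, and the documents do not support them.

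- **Missed repeats of the 4-hourly items can never be seen, so any difference between arms in re-examination would score as zero.** This depends on the unstated boundary. Under two of the three conventions the first repeat is visible.
- **At most a third of any prolonged labor is scored.** The definition in Section I is "prolonged labor (labors over 12 hours or labor that crosses the action line, may not be over 12 hours"; labors qualifying by the action line can be shorter, so 33% illustrates a 12-hour observation and is not a bound.
- **The later data are discarded.** Table 5 uses parameter values for each time period to score P2 and P3. They are unused only in this P1 score.
- **P1 is blind to repeated monitoring.** Five items are due 2 or 8 times in the window, and missed readings of these still show.

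The blank cells in the row for women arriving at 4 or 5 cm may be inherited or lost in conversion from PDF, so little weight rests on them.

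The remedy has limits too. A ratio of readings done to readings due does not fit the dichotomous outcomes and logistic regression in the plan without a cut-off or another model. Restricting to longer labors conditions on something that happens after admission and that labor management may affect. Both limits stand and are met in the fix.

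**Conclusion.** The concern holds as a mismatch between the name of a primary outcome and what it scores. Nothing after hour 4 counts for any item; that follows directly from the text. For 4 of the 11 scored items the window is one interval long, so the admission entry can satisfy them on the plain reading; on the other conventions only the first repeat is tested.

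The size for the trial as a whole cannot be stated, because the documents give no distribution of labor length. With 12 hours under observation, 8 of 24 half-hour slots and 1 of 3 rounds of the 4-hourly items are scored, the latter if hour 0 counts and the closing hour does not. The fault lies in the outcome definition; data capture is adequate. It should be settled before analysis, since the clock start, the boundary and the handling of labors under 4 hours are open and each allows more than one coding of a primary outcome.

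**What to change.** 1. Rename the current rule as completeness in the first 4 hours and keep it. State when the clock starts, whether the admission reading counts, and how labors ending before 4 hours are handled.
2. Add a true whole-labor outcome from the half-hourly values Tool 4 already extracts. For each item, count readings done out of readings due at the plan's own intervals over the extracted period. Turn this into yes/no with a cut-off fixed before the data are seen, which keeps the planned logistic regression with clustering, or analyse it as a clustered binomial proportion. State how the period ends when 10 cm is not recorded.
3. Report the 4-hourly repeats separately among labors long enough for one to be due. Label this supportive, because membership depends on labor length.
4. Apply the whole-labor rule to the row for women arriving at 4 or 5 cm.

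The cost is revised analysis-plan wording, a justified cut-off or model, and a little more programming. No new data collection or change to any monitoring interval is needed. Short labors will not contribute to the repeat-reading items.

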 - a. In paper-partograph sites, every day onsite records-management staff or, in the absence of such staff, the nurse in-charge will take **scans of the partographs**. These will be scanned to password-protected study laptops and the files will be saved directly to a secure Dropbox to which only study staff will have access.
 - b. At paper-partograph sites, each week onsite records-management staff or, in the absence of such staff, the nurse in-charge will take photographs the Ministry of Health approved **register**.
- 9) At the office, the study coordinator and data clerks will monitor ePartogram and partograph data in the ePartogram website and paper partograph Dropbox.
 - a. For paper partographs, the photos or scans of partographs will be uploaded to a computer.
 - b. When visiting facilities, the study coordinator will orient providers on how to record in the MOH register book, if this is not occurring to standard.
 - c. The study training covers how to enter record in the partograph or ePartogram app. A Jhpiego clinical study manager will provide a one-on-one orientation to the ePartogram for any new staff. On site visits, the study coordinator will help validate the most recent register book info by comparing to the medical record if one exists and discussing any discrepancies with staff during weekly calls.
 - d. Register data photographed from both study groups will be saved to the office computer. At office, a data entry clerk will follow the 'abstraction tool' to enter register data to a database.
- 10) Partograph reviewers who are student interns from Johns Hopkins School of Public Health and Johns Hopkins University will be hired to review each partograph and enter data from the partograph and ePartogram records to the study's Partograph Extraction Tool (Revised) (see Study Implementation section).
- 11) The study coordination and analysis team will conduct an analysis of data **after 20 partographs and 20 ePartograms** for each site and thereafter after every 200-400 partographs. This will be to assess for completeness of data to know whether we are on track to answer the research questions.

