 - a) In both study arms, providers will receive training on labor management and partograph usage per national and international WHO guidelines. Providers will be encouraged to consult their supervisor available when complications arise during labor, as per the standard-of-care. In the ePartogram study group only, a two-day training on ePartogram tablet use and maintenance will be given.
 - b) All providers in both study arms will be consented prior to the training.
 - c) ePartogram facilities will have the data transmitted over a cloud database accessible only to study staff.
 - d) An onsite facility staff will cover client identifiers and scan partographs and photograph registers for sending to a secure cloud folder. Client identifiers will be covered up prior to transmitting information.
 - e) Jhpiego study clinicians will access the scanned partographs and registers or ePartogram database online, and abstract the relevant data into the Partograph Extraction Tool 4 Revised and also the Register Review Tool 6. This data will be analyzed further by Jhpiego data analysts.
 - f) A study coordinator will be on call for any technical or software issues with the ePartogram, and backup tablets will be stored on site.
 - g) Note: if any clients in the ePartogram facility group are followed with a paper partograph, we will capture this info and consider this data to belong to the ePartogram group. We believe these providers would have been influenced by the use of the ePartogram in the facility.
 - h) Starting in second month, the study staff will collect qualitative interviews with SBAs, audio record, and transcribe for further analysis

Table 3

Study Timeline	Mar	Apr	May	June	July	Aug	Sept	Oct	Nov
Activity									
Ethical review by JHSPH and KEMRI	X	X	X						
Finalize training materials		X	X						
Facility and stakeholder orientation visits		X	X						
Facility stockup on supplies		X	X						
Data collector training		X	X						
Provider trainings			X	X					
Data collection			X	X	X				
Partograph Review and Data analysis			X	X	X	X	X		
Dissemination Meeting								X	

Table 4. Tools

The following are data collection or abstraction tools to be used in this study.

Tool No.	Tool Name	Description

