P2. Decision-making and actions taken to maintain normal labor (Tool 4)	Data on each partograph parameter will be entered for each time period, as well as actions taken in labor. Jhpiego clinical rules will be applied to the data in the extraction database to determine appropriate clinical actions for a labor without any complication. This is a binary variable.	Labors in which Section 3 marked as “Normal Labor”	First, we will examine the frequency/prevalence of each clinical action taken in normal labor and compare between the two study groups. Second, we will carry out same analysis as for Objective P1.
P3. Detection, decision-making and action to address deviations from normal labor and complications arising during labor—for ‘slow’ labor, prolonged labor, obstructed labor and cephalo-pelvic disproportion	Data on each partograph parameter will be entered for each time period, as well as actions taken in labor. Jhpiego clinical rules will be applied to the data in the extraction database to determine appropriate clinical actions for a labor with a specific complication. This is a binary variable.	Labors in which Section 3 marked “Slow labor, prolonged labor, obstructed labor or cephalo-pelvic disproportion”	First, we will examine the frequency/prevalence of each clinical action taken in selected complications and compare between the two study groups. Second, we will carry out same analysis as for Objective P1.
-- for all complications (Tool 4)	Same as above. A composite variable will be created for all complications. This is a binary variable.	Labors in which Section 3 marked as ANY complication	First, we will examine the frequency/prevalence of each clinical action taken in all

			complications and compare between the two study groups. Second, we will carry out same analysis as for Objective P1.
S1. Is facility use of ePartogram (vs. paper-partograph) associated with lower rate of...?			
From the Register Analysis			
Neonatal deaths <24 hours and (Tool 5)	Number of early neonatal deaths. This is a count variable.	All live births	We will compare means using t-tests across 2 groups. Next, we will use unadjusted regression models that account for clustering (correlation) of data within the facility. Poisson regression with offset term (or another appropriate model to be explored) will be used for bivariate and multivariable analysis.

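### P1 timeliness over labor is left to reviewers who are not stated to be masked, with no numeric tolerance, although the Tool 4 values would let one program score both arms alike

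*Combined protocol and SAP*

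**What the plan says.** P1 is one of three primary questions (section I). Its over-labor component is defined in section V.C.4, Table 5. A labor scores 'yes' if all 11 items (the 12 listed, less urine volume) are measured at their set intervals during the first four hours.

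- **Who decides timeliness.** The cell says the "reviewer will determine for each item if occurred within the interval".
- **The standard.** Earlier in the same cell, the aim is to "determine whether this was done to a large extent on time". No number is attached.
- **Conditional items.** Two of the 11 have no fixed interval: "amniotic fluid if membranes rupture, moulding when present head descent every 2 hours" (head descent, also caught in this run of text, does have one).
- **Database wording.** The cell opens by saying that each parameter is entered to the database and that frequency is considered under the Jhpiego Clinical Rules.
- **What is extracted.** Table 4 describes Tool 4 as allowing "data entry on the actual values of the measurements are recorded for 13 parameters", and adds: "These data will be recorded for each 30 minute interval for the duration of the active stage of labor".
- **P2 and P3.** Table 5 says: "Data on each partograph parameter will be entered for each time period, as well as actions taken in labor". It then states that the clinical rules are applied to the extraction database. The cases are those labors with a given marking in Section 3.
- **Who reviews.** Section III.A, item 10 has "Partograph reviewers who are student interns". Section V.C.1, item e says "Jhpiego study clinicians will access the scanned partographs".
- **Masking.** The blinding answer in section V.C.6.f covers only in-charges and providers.

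**The concern.** Without a numeric tolerance, two reviewers could score the same chart differently and both follow the plan. A reviewer who opens an ePartogram record also knows which arm it belongs to. If leniency differs between record types, even unintentionally, the difference enters a primary outcome as an apparent effect of the ePartogram or hides a real one. The all-items requirement makes this worse, because one disputed item changes the score for the whole labor. The discretion seems avoidable, since the extracted data are already laid out on a 30-minute grid and P2 and P3 are to be scored from that database.

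**Working it through.** The plan gives no figure for reviewer error or scoring agreement, so there is nothing of its own to reproduce here. The sample size rests on the P3 indicator and is unaffected.

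**Step 1: can the rule be coded from Tool 4?** Take blood pressure as one item, so that the list has 12 items and 11 remain without urine volume. The number of 30-minute cells in four hours at the intervals in Table 5 is:

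- Fetal heart rate, contractions and pulse, every 30 minutes: 3 × 8 = 24
- Head descent and temperature, every 2 hours: 2 × 2 = 4
- Cervical dilation, blood pressure, urine protein and acetone, every 4 hours: 4 × 1 = 4

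These nine items need 24 + 4 + 4 = 32 scheduled entries, all on the Tool 4 grid, and a program can score them directly. For a half-hourly item the question becomes whether each of eight cells is filled, plus a stated number that may be missing. The other two items, amniotic fluid and moulding, need a written rule. For moulding, for example, an empty cell could mean absent or not assessed. A reviewer working from the same record faces the same ambiguity.

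**Step 2: how far does the all-items rule magnify a scoring difference?** The text has the reviewer decide per item, so the item is the unit. Assume 11 independent items, all required, each accepted with probability *a*. Then P(yes) = *a*^11.

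- *a* = 0.95: 0.95^11 = 0.569
- *a* = 0.96: 0.96^11 = 0.638
- Difference: 6.9 points, from 1 point per item

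**Step 3: what leniency does that imply?** Let *q* be the true on-time probability per item, equal in both arms, and *f* the share of late items passed in one arm only. Acceptance in that arm is *q* + (1 − *q*)*f*. With *q* = 0.95, reaching 0.96 needs *f* = 0.01/0.05 = 0.20. So the 1-point difference means passing one late item in five in one arm and none in the other.

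**Step 4: range over assumed inputs.** The false difference is [*q* + (1 − *q*)*f*]^11 − *q*^11.

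| *q* | *f* = 0.10 | *f* = 0.20 | *f* = 0.30 |
|---|---|---|---|
| 0.85 | 3.6 points | 7.8 points | 12.8 points |
| 0.90 | 4.1 points | 8.6 points | 13.6 points |
| 0.95 | 3.4 points | 6.9 points | 10.7 points |

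Every *q* and *f* is assumed. The table shows sensitivity and does not predict bias, and the documents do not indicate which arm would be favored.

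**The case against.** The strongest reply is that P1 is already meant to be derived from the database. The cell speaks of database entry and the Clinical Rules, and checking an entry against a listed interval involves little judgement for nine of the 11 items. This stands in part: it shows that the cell is unclear, not that reviewers alone score P1. But the reviewer clause is in the same cell, and the on-time standard has no number, so the discretion remains as written.

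A reader might infer several stronger things that the documents do not support:

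- **That every record shows its arm.** Paper partographs used at ePartogram sites count in the ePartogram group (sections III.A item 7c, V.C.1 item g and V.C.6.f). An ePartogram record reveals the arm, but a paper record alone does not.
- **That reviewers are declared unblinded.** The text never says so. The point rests on the lack of any masking statement, and part of section X (Study Management) was not available to check.
- **That the developer's own clinicians judge the outcome.** One section names student interns and another names Jhpiego clinicians. That contradiction is unresolved.
- **That the effect should be computed per reading.** Over the 24 half-hourly readings, 0.95^24 = 29.2% against 0.96^24 = 37.5%, or 8.3 points. But the text has the reviewer decide per item, and a strict all-24 rule disregards the looser on-time wording.
- **That the P2 and P3 denominators are reviewer-assigned.** The form containing Section 3 is not among the documents, and they do not say how it is marked.
- **That a program removes the bias.** Someone who can see the record type would still read each plotted entry and choose its 30-minute cell. Nor can a program detect charts filled in afterwards, a problem the Background raises.

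**Conclusion.** The concern holds for P1 timeliness over labor. As written, a discretionary step with no numeric tolerance helps determine a primary outcome, by reviewers not stated to be masked, when the extracted data would support a fixed rule. P1 at admission involves no interval judgement. P2 and P3 scoring is already rule-based, apart from the open question about the Section 3 label.

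The size of any bias cannot be estimated from the documents. The illustration of 57% against 64% assumes independent items, all 11 required, and a leniency difference that no source supplies. It establishes only that the composite magnifies small differences in scoring. The change should be made, because a better method is available from data the study already plans to extract.

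**What to change.** Amend the P1 cell of Table 5 as follows:

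1. Reviewers enter Tool 4 values by 30-minute interval and make no on-time decision.
2. One program derives P1 on-time status from those values, identically in both arms.
3. Before any comparison by arm, fix in writing the tolerance that replaces the phrase about being largely on time, and the scoring rules for amniotic fluid and moulding, including how empty cells are treated.
4. State how the Section 3 normal/complication label is assigned. If reviewers assign it, derive it from the same data by the same kind of rule.
5. Reconcile sections III.A item 10 and V.C.1 item e on who extracts the data.

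The cost is modest programming and a short text change, with no extra reader, no new data collection and no change in sample size. Transcription by people who can see the record type would remain, and the report should state that limitation.
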